### **7.2.3 Fresh specimens in RNA later solution**

All sites which have recruited 25 or more patients should additionally provide fresh tissue specimens from the normal oesophagus, Barrett's oesophagus, and fundus (3 in total), using RNA Later solution which will be supplied by the Trial Laboratory and should be submitted to the laboratory as per the SOPs provided. This is compulsory for sites which have recruited 25 or more patients as these tissues are required for secondary endpoints and these larger sites contribute 80% of the patients. DNA and RNA will be extracted from additional samples in RNA later (although in occasional circumstances paraffin embedded material may be used when the former isn't available) for SNP analysis and micro array analysis.

### **7.2.4 Blood samples**

Blood samples are collected from all patients at baseline, between 4 and 6 years post randomisation, plus at 8 and 10 (if patients re-consented) years post randomisation to assess cancer and cardiovascular risk factors. The remainder will be stored for analysis of circulating genetic mutations as and when reliable assays become available. Patients who did not provide a blood sample at any of these visits or whose sample was collected but found to be clinically unsuitable will be asked to provide a blood sample at the next follow-up visit. The blood tubes and packaging to post samples to the Trial Laboratory are provided by the laboratory. The procedure for taking blood is provided with the supplies. Samples should not be taken from patients who are known to be HIV, HBV or HCV positive. Samples which may contain any other infectious material should not be submitted.

## **7.3 Helicobacter testing**

Helicobacter testing can be completed in two ways; either a blood or biopsy sample (preferred) maybe taken for diagnosis at local pathology lab or a Clo test may be taken on a biopsy sample during the endoscopy. In the case of the latter, the result this should be recorded in the relevant section of the Endoscopy and Pathology CRF. If the initial biopsy test is positive then patients should be tested post treatment with a breath test. If the Clo test is the initial test and it is negative it is preferable that serum testing is done in these individuals at some point during the study. This may be done from the donated serum. All patients should have their Helicobacter Pylori status checked at least once during the study. At the end of the trial all patients should have Helicobacter Pylori status noted even if eradicated (as eradication can be unsuccessful in 10% of cases).

## **7.4 Clinical reporting of exploratory research assay results**

The results of the AspECT trial research assays are exploratory and are not intended to influence the individual patient's medical care. Findings will not be reported routinely to the responsible clinician except in the unlikely event that the result might be beneficial to the patient's clinical management.

## 7.5 Trial sample retention at end of study

Trial samples collected from AspECT patients will fall under the custodianship of the ChOPIN trial which runs under its own separate approval, REC Ref: 06/Q1603/07 (East London Research Ethics Committee 1). The CI for ChOPIN is also [name]. Laboratories are instructed to retain any surplus samples pending instruction from the Chief Investigator on use, storage or destruction. It is possible that new or alternative assays may be of future scientific interest. At the end of the research study, any surplus samples may be retained for use in other projects that have received ethical approval. Hence, any surplus study samples may be transferred to a licensed tissue bank where they will be managed in accordance with applicable host institution policies and the Human Tissue Act (HTA) requirements.

## 7.6 Withdrawal of consent for sample collection and/or retention

A patient may withdraw consent to provide samples for research at any time without giving a reason. The Investigator must ensure that their wishes are recorded in their medical record and will inform the Trial Office accordingly. The investigator should discuss with patients the valuable use of samples that have already been provided and under circumstances where these samples have already been processed and anonymised, it would not be possible to destroy such samples.

# 8 INVESTIGATIONAL MEDICINAL PRODUCTS (IMPs)

## 8.1 Name of IMPs

Esomeprazole (Nexium)  
Aspirin

## 8.2 Treatment dose

Patients receive either continuous PPI 20mg/day or continuous PPI 80mg/day with or without aspirin 300mg/day. No washout period was required for individuals already on aspirin or PPI to allow baseline blood tests and biopsy to be assessed easily.

If patients are on low dose aspirin for medical reasons (i.e. previous IHD or CVA rather than self-prescribed) they were randomised to either continuous PPI 20mg/day or continuous PPI 80mg/day arms. They are allowed to continue to take their aspirin therapy.

Patients are allowed to default from the prescribed drugs or doses for up to six months at one time or for a total of 12 months during the length of the trial. A drug holiday longer than this time period will be deemed a protocol violation but the patient should still be kept on follow-up.

## 8.3 Duration of treatment

Patients should remain on trial medication for the duration of follow-up period of 8 years or 10 years (if the patients re-consented) unless they withdraw or are withdrawn from treatment or withdraw consent.

## 8.4 Special precautions

### *Aspirin*

Aspirin - Gastro-intestinal

The risk of significant gastro-intestinal complications associated with NSAIDs is not completely eliminated by low dose aspirin. Ulcers and upper GI perforations, ulcers or bleeds (PUBs) did occur in osteoarthritis patients treated with aspirin.

Aspirin - Hepatic

A patient with symptoms and/or signs suggesting liver dysfunction, or in whom an abnormal liver function test has occurred, should be evaluated and treatment should be discontinued if persistently abnormal tests are detected (bilirubin > 100, ALT > 150 and caution used when any enzymes are 3x upper limit of normal).

Aspirin - Effects on ability to drive and operate machinery

Patients who experience dizziness or somnolence whilst taking aspirin should refrain from driving or operating machinery.

***Esomeprazole***

Patients with rare hereditary problems of fructose intolerance, glucose-galactose malabsorption or sucrase-isomaltase insufficiency should not take this medicine.

**Esomeprazole - Hepatic insufficiency**

The metabolism of esomeprazole in patients with mild to moderate liver dysfunction is similar to that in patients with symptomatic Gastro Oesophageal Reflux Disease (GORD) with normal liver function. The metabolic rate is decreased in patients with severe liver dysfunction resulting in a doubling of the area under the plasma concentration-time curve of esomeprazole. Therefore, a maximum dose of 20mg should not be exceeded in patients with severe dysfunction i.e. advanced liver failure with a combination of ascites, encephalopathy and varices and other biochemical or haematological features. Esomeprazole or its major metabolites do not show any tendency to accumulate with once daily dosing.

**Esomeprazole - Renal Insufficiency**

No studies have been performed in patients with decreased renal function. Since the kidney is responsible for the excretion of the metabolites of esomeprazole but not for the elimination of the parent compound, the metabolism of esomeprazole is not expected to be changed in patients with impaired renal function.

***Other special precautions***

**Asthma:** Patients with asthma or other respiratory disease were entered into the trial provided that there was no history of side effects or complications when taking aspirin. If a patient with asthma was randomised to one of the aspirin arms of the trial, then monitoring of their condition may have been indicated. If the patient's asthma worsens due to the aspirin, then the aspirin should be ceased.

**Hepatic and renal function:** If hepatic and renal function tests are indicated, and the result is above normal limits for any test, then the patient should not have been entered into the trial if the local investigator feels it is appropriate. Please note, hepatic and renal function tests are not mandatory. If done, we consider ALT, GGT and bilirubin should not be over x3 the upper end of the normal range. In that case we would recommend cessation of aspirin especially if the platelets are less than 60 and the INR is prolonged greater than 1.6. If further advice is required, please contact the Trial Office on [name].

**Osteoporosis:** The potential risk of osteoporosis/osteoporotic fracture including hip fracture, in relation to PPI (including esomeprazole) exposure has been discussed in the published literature but no causal link has been established. However, patients with suspected osteoporosis will be investigated by bone scan. If the results of the bone scan indicate a requirement for therapy according to local guidelines, they may be prescribed calcium and vitamin D or indeed bisphosphonates according to local practice and this must be noted in the CRFs.

**Cardiac Disease:** There is caution required for those on clopidogrel as esomeprazole may decrease bioavailability. Patients should be advised by their local investigator. In the management of these patients the SmPC of clopidogrel should be considered: <http://www.medicines.org.uk/emc/medicine/24206>. Trial staff are asked to document patients who are prescribed clopidogrel using the clopidogrel CRF.

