### **Hepatic Insufficiency**

Salicylate is mainly eliminated by hepatic metabolism – the metabolites including salicylic acid, salicyl phenolic glucuronide, salicylic acyl glucuronide, gentisic acid and gentisuric acid. As a result of zero order kinetics, plasma steady state salicylate concentrations increase disproportionately with dose. Aspirin should be avoided in patients with severe hepatic impairment (ALT > 150 or bilirubin over 100).

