### **8.9 (Potential) Drug Interactions**

#### ***Aspirin***

Alcohol and corticosteroids may enhance the effects of aspirin on the gastrointestinal tract. Aspirin may enhance the effects of coumarin anticoagulants and oral hypoglycaemics of the sulphonylurea type. The toxicity of methotrexate may be enhanced by concomitant use of aspirin. Aspirin diminishes the action of uricosurics. Post marketing reports have suggested that the plasma concentration of lithium could be increased whilst taking aspirin [25]. Stop aspirin if there is a chance of bleeding, such as INR > 1.6 or platelets < 60. If INR is between 1.3 and 1.6 the local clinician can judge the collective risk/benefit of aspirin use or if in doubt ask the Trial Office. If the patient is also on other anticoagulants such as warfarin, aspirin should only be used if necessary for other conditions such as CVA prophylaxis or post-coronary stent insertion as prescribed by the physician caring for this problem.

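### Protocol 8.4 gives two different aspirin instructions for a liver test above three times normal: caution in one paragraph, recommended cessation in another

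*Protocol*

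**What the plan says.** Two paragraphs of Protocol 8.4 deal with aspirin and abnormal liver tests.

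- **Aspirin - Hepatic:** "treatment should be discontinued if persistently abnormal tests are detected (bilirubin > 100, ALT > 150", followed in the same bracket by "caution used when any enzymes are 3x upper limit of normal".
- **Other special precautions, hepatic and renal function:** "we consider ALT, GGT and bilirubin should not be over x3 the upper end of the normal range". The next sentence says what follows if they are: "we would recommend cessation of aspirin especially if the platelets are less than 60 and the INR is prolonged greater than 1.6". The paragraph also says that these tests are not mandatory, and it offers advice from the Trial Office.

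Two other places touch the same ground. Protocol 1.3 (Hepatic Insufficiency) says aspirin should be avoided in "severe hepatic impairment (ALT > 150 or bilirubin over 100". Protocol 8.9 (Drug Interactions, aspirin) says "Stop aspirin if there is a chance of bleeding, such as INR > 1.6 or platelets < 60" and leaves an INR between 1.3 and 1.6 to the local clinician.

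None of the four places refers to another or says which prevails. The SAP contains no liver-test, platelet or INR rule.

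**The concern.** The same trigger, an enzyme above three times normal, carries two different actions a few paragraphs apart. Two sites that both follow 8.4 in good faith could handle the same result differently: one keeps the patient on aspirin and watches, the other stops it. Aspirin is planned for 8 or 10 years, and 8.4 asks investigators to go through the special precautions at each return visit, so these are working instructions.

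What is at stake is, first, consistent safety handling. Second is aspirin exposure: SAP 8.8 will describe withdrawal rates and dose over time, and SAP Appendix 1 requires at least 6 months of aspirin at the randomised dose for the per-protocol set (less only where an event comes sooner).

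**Working it through.** The plan states no figure to reproduce, so the check sets the two 8.4 paragraphs side by side and reads the same result under each.

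| | Aspirin - Hepatic | Other special precautions |
|---|---|---|
| Tests with a stopping figure | bilirubin, ALT | ALT, GGT, bilirubin |
| Scale for stopping | absolute: 100 and 150, no units given | multiple of the upper limit |
| Must the abnormality persist? | yes | not mentioned |
| Action above 3x normal | caution (enzymes only) | cessation recommended |

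The right-hand column is read as applying to any one of the three tests.

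**GGT.** GGT is an enzyme, so above 3x normal the first paragraph gives caution, and it has no stopping figure for GGT. The second recommends cessation. No normal range has to be assumed.

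**ALT.** Let L be the local upper limit, which the documents do not give. The conflict band is 3L < ALT ≤ 150, which is non-empty when L < 150/3 = 50.

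- L = 30: 3L = 90, band 90 to 150.
- L = 40: 3L = 120, band 120 to 150.
- L = 50: 3L = 150, no band.
- L = 55: 3L = 165. The order reverses: results from 150 to 165 pass the first paragraph's figure but not the second's multiple.

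**Bilirubin.** The band is 3L < bilirubin ≤ 100, non-empty when L < 100/3 ≈ 33.

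- L = 17: 3L = 51, band 51 to 100.
- L = 21: 3L = 63, band 63 to 100.

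Here the first paragraph gives no action at all, because its caution clause names enzymes only.

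**Persistence.** Take a single ALT of 160 with an assumed L of 40. It exceeds 120, so the second paragraph recommends cessation. It also exceeds 150, but the first paragraph discontinues only if the abnormality persists.

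**Platelets and INR (secondary).** 8.4 joins platelets < 60 and INR > 1.6 with *and*, introduced by *especially*; 8.9 joins the same two figures with *or*. A patient with platelets < 60 and INR ≤ 1.6 is told to stop by 8.9. 8.4 does not tell that patient to continue, so the two can be followed together. A site reading 8.4 alone could still take both findings as needed.

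**The case against.** The best defence is that this is guidance within clinical discretion, not an algorithm. The tests are optional, the cessation sentence is worded as a recommendation, the Trial Office can be asked, and Protocol 6.1 lets the investigator withdraw treatment in the patient's interest. All of that stands and limits the consequence. It does not tell a site which paragraph to follow once a test has been done.

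Some stronger readings are tempting and do not hold:

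- *That 8.4 and 8.9 contradict each other on platelets and INR.* In 8.4 the pair adds emphasis to a cessation already recommended for the liver result; it is not a condition for stopping. 8.9 is a separate bleeding rule.
- *That 1.3 conflicts with 8.4 because one uses* or *and the other a comma.* Both give 150 for ALT and 100 for bilirubin, and the comma does not require both to be exceeded. Only the persistence wording differs.
- *That reasons for stopping aspirin will go unrecorded.* Protocol 6.1 requires the reason on the End of Treatment form, and 8.5 requires dose changes and breaks on a Change of Treatment form, whichever threshold was used.

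**Conclusion.** The contradiction inside Protocol 8.4 is real and nothing else in the documents resolves it. It is certain for GGT. For ALT and bilirubin it depends on local upper limits: below 50 for ALT and below about 33 for bilirubin, on the assumption that local units match those intended for 150 and 100. The platelet and INR wording is a clarity point only.

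How many patients are affected cannot be estimated, because the documents do not say how often these tests are done or are abnormal. A reader might infer that the primary result is compromised. It is not: the primary analysis is by intention to treat (Protocol 14, SAP 7), so neither its analysis set nor the sample size changes. The effect is on safety handling and aspirin exposure. The text is wrong as written and should be corrected, with modest consequence.

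**What to change.** The sponsor must reconcile the two paragraphs of 8.4 into one set of aspirin instructions. That text should:

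- state one action for each liver-test result, on one scale with units;
- name the tests covered, and say whether any one of them is enough;
- say whether the abnormality must persist;
- say explicitly whether the platelet and INR findings are needed jointly or singly.

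Sections 1.3 and 8.9 should then be aligned with it and cross-refer to it. Which threshold and action to adopt is for the sponsor and its clinicians.

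The cost is a wording amendment and a note to sites; no analysis changes. It helps only while patients are still on aspirin, and the Protocol puts the last visit at 28 February 2017 plus three months. After that, the report can only note the differing instructions when it describes aspirin withdrawals.

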**Withholding drugs prior to endoscopy**

There is no need to withhold esomeprazole therapy prior to endoscopy. Aspirin, as with all antiplatelet drugs, can aggravate bleeding in an unpredictable way. BSG guidelines regarding suspension of aspirin prior to endoscopy should be followed. The decision lies with the local PI.

Investigators should ask specifically about these special precautions on each return visit and record this on the Follow-Up CRFs.

## **8.5 Dose modification**

***Aspirin dose reduction:***

Dyspepsia is a risk factor for NSAID GI bleeding (Aalycke, 1999). If the patient has dyspepsia and it is thought this might be due to aspirin therapy the patient may decrease from 300mg/day to 150mg/day at the decision of the local PI. If symptoms still persist after 3-7 days the patient can be decreased to 75mg/day. If the symptoms have not resolved after a further 3-7 days the patient may take aspirin 75mg twice a week (every 3 days or on specified days

e.g. Thursday and Sunday). Further symptoms or a frank GI bleed (malaena or vomiting of blood) should be clinically reviewed and may lead to immediate cessation of aspirin.

#### ***Esomeprazole dose changes:***

If the patient is receiving 80mg/day of esomeprazole and expresses a wish to take a lower dose, the dose can be changed to 40mg/day indefinitely at the decision of the local PI. This should be prescribed as 20mg BD.

Alternatively if the patient is on 20mg/day of esomeprazole and still has reflux symptoms, the dose can be increased to 40mg/day indefinitely. This should be prescribed as 20mg BD.

Patients are allowed 6 months of another treatment option or a break from treatment for any 6 month period or 12 months in total over the entire trial length of up to 10 years.

All dose changes or breaks in treatment must be documented on a Change of Treatment Form.

### **8.6 Compliance**

Compliance should be checked by asking patients to bring all their unused/remaining trial medicines (empty, opened or unopened) with them when they visit the hospital pharmacy to pick up their new drug supply.

### **8.7 Management of overdose**

#### ***Aspirin***

Symptoms of overdose include dizziness, tinnitus, sweating, nausea, vomiting, hyperventilation, fever and restlessness. Treatment includes gastric lavage or emesis, rehydration and forced alkaline diuresis. Serum electrolytes, particularly potassium and acid base balance should be treated accordingly. Haemo or peritoneal dialysis may be necessary in the case of severe overdose.

#### ***Esomeprazole***

There is very limited experience to date with deliberate overdose. The symptoms described in connection with 280mg were gastrointestinal symptoms and weakness. Single doses of 80mg esomeprazole were uneventful. No specific antidote is known. Esomeprazole is extensively plasma protein bound and is therefore not readily dialyzable. As in any case of overdose, treatment should be symptomatic and general supportive measures should be utilised.

### **8.8 Concomitant medication and non-drug therapies**

Concomitant medication may be given as medically indicated. At every annual follow-up, all patients are asked to provide a complete list of prescription and over-the-counter medications that have been taken for more than 2 weeks during the last 12 months. Details (including indication, doses, frequency and start / stop dates) of concomitant medication taken during the trial until the completion of the off-study visit must be recorded in the medical record and the appropriate CRF.

### **8.9 (Potential) Drug Interactions**

#### ***Aspirin***

Alcohol and corticosteroids may enhance the effects of aspirin on the gastrointestinal tract. Aspirin may enhance the effects of coumarin anticoagulants and oral hypoglycaemics of the sulphonylurea type. The toxicity of methotrexate may be enhanced by concomitant use of aspirin. Aspirin diminishes the action of uricosurics. Post marketing reports have suggested that the plasma concentration of lithium could be increased whilst taking aspirin [25]. Stop aspirin if there is a chance of bleeding, such as INR > 1.6 or platelets < 60. If INR is between 1.3 and 1.6 the local clinician can judge the collective risk/benefit of aspirin use or if in doubt ask the Trial Office. If the patient is also on other anticoagulants such as warfarin, aspirin should only be used if necessary for other conditions such as CVA prophylaxis or post-coronary stent insertion as prescribed by the physician caring for this problem.

#### ***Esomeprazole***

The decreased intragastric acidity during treatment with esomeprazole might increase or decrease the absorption of drugs if the mechanism of absorption is influenced by gastric acidity. In common with the use of the other inhibitors of acid secretion or antacids, the absorption of ketoconazole, itraconazole and erlotinib can decrease and the absorption of digoxin can increase during treatment with esomeprazole. Concomitant treatment with omeprazole (20 mg daily) and digoxin in healthy subjects increased the bioavailability of digoxin by 10% (up to 30% in two out of ten subjects)

Esomeprazole inhibits CYP2C19, the major esomeprazole metabolising enzyme. Thus, when esomeprazole is combined with drugs metabolised by CYP2C19, such as diazepam, citalopram, imipramine, clomipramine, phenytoin etc., the plasma concentrations of these drugs may be increased and a dose reduction could be needed. This should be considered especially when prescribing esomeprazole for on-demand therapy. Concomitant administration of 30mg esomeprazole resulted in a 45% decrease in clearance of the CYP2C19 substrate diazepam.

Concomitant administration of 40mg esomeprazole resulted in a 13% increase in trough plasma levels of phenytoin in epileptic patients. It is recommended to monitor the plasma concentrations of phenytoin when treatment with esomeprazole is introduced or withdrawn. Concomitant administration of 40mg esomeprazole to warfarin-treated patients in a clinical trial showed that coagulation times were within the accepted range. However a few isolated cases of elevated INR of clinical significance have been reported post marketing, during concomitant treatment. Monitoring is recommended when initiating and ending concomitant treatment.

Esomeprazole has been shown to have no clinically relevant effects on the pharmacokinetics of amoxycillin or quinidine.

There is no firm evidence suggesting a required change to the way esomeprazole or clopidogrel are prescribed but the MHRA suggests the concomitant use of clopidogrel and omeprazole or esomeprazole is to be discouraged unless considered essential.

See *Nexium IB and Summary of Product Characteristics* as well as <http://www.mhra.gov.uk/Publications/Safetyguidance/DrugSafetyUpdate/CON076501> for further information. Any important updates may be provided by newsletters.

Esomeprazole is metabolised by CYP2C19 and CYP3A4. Concomitant administration of esomeprazole and a CYP3A4 inhibitor, clarithromycin (500 mg bid) resulted in a doubling of the exposure (AUC) to esomeprazole. Dose adjustment of esomeprazole is not required.

For further information please refer to the *Investigator Brochure (IB)* and *Summary of Product Characteristics (SmPC)* provided. Copies are available from the Trial Office.

